### 3 INVESTIGATIONAL PLAN

#### 3.1 Overall Study Design and Plan

[figure not shown]
This is a Phase 2, randomized, double-blind, placebo-controlled, dose-finding study to assess the efficacy, safety, tolerability, PK, and PD of orally administered vadadustat in Japanese subjects with anemia secondary to NDD-CKD.

The study has a planned enrollment of 48 subjects to be enrolled at approximately 25 sites in Japan. There will be 16 subjects in each of the 3 tablet-count groups.

An overview of the study design is presented in [Figure 1](#).

Figure 1: Overview of Study Design

\* For subjects who develop an excess Hb response during the primary efficacy period, the number of tablets of study drug will be decreased (see Section 8.2.4). For these subjects, the number of tablets of vadadustat initiated at the Week 6 visit will be lower than indicated.

The study will include the following periods:

- Eligibility screening period (up to 4 weeks)
- Primary efficacy period (6 weeks; Weeks 1 to 6)
- Dose adjustment and maintenance period (10 weeks; Weeks 7 to 16)
- Follow-up period (2 weeks; Weeks 17 and 18)

Subjects will participate in a screening period (4 days to 4 weeks) to determine study eligibility, and eligible subjects will be randomized following the screening period.

Using a central randomization system, subjects will be randomized 1:1:1 to receive 1, 2, or 4 tablets at their baseline visit (Day 1). Within each tablet-count group, subjects will be randomized 3:1 to receive vadadustat (150, 300, or 600 mg vadadustat) or placebo. See the protocol section 8.2.2 for information regarding the randomization scheme.

Study drug treatment will be administered during a 6-week primary efficacy period. See the protocol section 8.2.4 for information on study drug administration. The primary efficacy period includes fixed-dose treatment to establish a dose-response relationship. However, if Hb level increase rapidly or if the Hb level exceeds 13.0 g/dL, the study drug dose can be decreased or interrupted (see the protocol section 8.2.4).

After completing the primary efficacy period, subjects will continue to a 10-week dose adjustment and maintenance period (see the protocol section 8.2.5). Subjects receiving placebo will be switched to vadadustat, and study drug dose will be adjusted to achieve a target Hb of 10.0-12.0 g/dL based on dose adjustment guidelines (see the protocol section 8.2.5).

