#### 4.9.2 Treatment-Emergent Outliers analysis

The purpose of this analysis is to identify the treatment Emergent outliers by each prescribed dose at each period. The definition of prescribed doses is the subjects with latest dose amount at planned visit when dose change. e.g. if at Week 2 with dose 600 mg and dose reduced to 450 mg at week 4, then visit of prescribed dose for VADA 450 was assigned to Week 4.

However, if subject had dose reduction on 150 mg or had interruption of study medication, the prescribed dose will be considered as 0 mg.

Only treatment-emergent outliers will be counted but outliers at the baseline and screening visits will be excluded.

The following components will be analyzed by primary efficacy period and dose adjustment and maintenance period for all subjects and for subjects with non-elevated values at baseline:

- Non-elevated at baseline definition for each component
  - Systolic Blood Pressure <140 mmHg
  - Diastolic Blood Pressure <90 mmHg
  - Heart Rate <100 bpm
  - Potassium <4 mEq/L

The following component with following criteria will be applied.

- Systolic Blood Pressure
  - Any SBP  $\geq 160$  to <180 mmHg
  - Any SBP  $\geq 180$  mmHg
  - Any SBP increase from baseline  $\geq 20$  to <40 mmHg
  - Any SBP increase from baseline  $\geq 40$  mmHg
- Diastolic Blood Pressure
  - Any DBP  $\geq 100$  to <110 mmHg
  - Any DBP  $\geq 110$  mmHg
  - Any DBP increase from baseline  $\geq 10$  to <20 mmHg
  - Any DBP increase from baseline  $\geq 20$  mmHg
- Heart Rate
  - Any pulse  $\geq 100$  to <120 bpm
  - Any pulse  $\geq 120$  bpm
  - Any pulse increase from baseline  $\geq 20$  to <30 bpm
  - Any pulse increase from baseline  $\geq 30$  bpm
- Potassium
  - Any Potassium >5.5 to 6.0 mEq/L
  - Any Potassium >6.0 to 6.5 mEq/L
  - Any Potassium >6.5 mEq/L
  - Any Potassium increase from baseline >0.5 to 1.0
  - Any Potassium increase from baseline >1.0 to 1.5 mEq/L
  - Any Potassium increase from baseline > 1.5 mEq/L

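### SAP 4.9.2 files readings taken at a dose-change visit under the new dose (or 0 mg), although they reflect the dose taken before that visit

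*SAP*

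**What the plan says.** Amendment 3 added section 4.9.2 to the SAP. It states its aim as follows: "The purpose of this analysis is to identify the treatment Emergent outliers by each prescribed dose at each period". The dose label is then defined: "The definition of prescribed doses is the subjects with latest dose amount at planned visit when dose change". A worked example follows for a subject on 600 mg at Week 2: "dose reduced to 450 mg at week 4, then visit of prescribed dose for VADA 450 was assigned to Week 4". A second rule covers stopping: "if subject had dose reduction on 150 mg or had interruption of study medication, the prescribed dose will be considered as 0 mg".

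The results are split by study period: "The following components will be analyzed by primary efficacy period and dose adjustment and maintenance period for all subjects", and again for subjects whose value was not elevated at baseline. The section has no lag, makes no reference to the dose taken before the reading, and says nothing about placebo or Week 6.

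Section 3.1 supplies the design. It lists "Primary efficacy period (6 weeks; Weeks 1 to 6"), followed by Weeks 7 to 16 for dose adjustment and maintenance. Placebo subjects change to vadadustat once the first period is complete. The footnote to Figure 1, written about subjects with an excess Hb response, says that "the number of tablets of vadadustat initiated at the Week 6 visit will be lower than indicated". It therefore places the start of the post-switch tablets at the Week 6 visit.

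**The concern.** A blood pressure, pulse or potassium value recorded at the visit where the dose is changed reflects the treatment taken up to that visit. The new dose cannot have produced it. A table meant to show outliers by dose should count the value under the old dose, but the example in 4.9.2 counts it under the new one.

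The trial is meant to choose a Phase 3 starting dose, so safety by dose matters. Section 4.9.2 is also the only place in the current SAP that counts blood pressure and heart rate against thresholds. Section 4.8.5.1 gives means, changes and a plot. With 12 planned subjects per arm, a few misplaced readings can alter a column visibly.

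**Working it through.** **1. The rule applied to each kind of dose change.** The SAP column follows from the definition, the example and the 0 mg rule in 4.9.2. The last column is the treatment taken up to the reading.

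| Reading at | Counted by the SAP under | Treatment it reflects |
|---|---|---|
| Week 4, 600 mg reduced to 450 mg (SAP example) | 450 mg | 600 mg |
| Visit where drug is interrupted | 0 mg | dose before interruption |
| Visit where dose is reduced from 150 mg | 0 mg | 150 mg |
| Later visit while still off drug | 0 mg | none (label correct) |
| Visit where drug is restarted | restarted dose | none |
| Visit where dose is increased after Week 6 | higher dose | lower dose |

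Five of the six rows are misattributed. The 0 mg label is right for readings taken while drug is off and wrong only at the visit where it is stopped.

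**2. Direction.** Section 3.1 describes only reductions or interruptions in the primary efficacy period, prompted by the Hb response. There, readings move from higher doses to lower doses or 0 mg. After Week 6 the dose is adjusted towards an Hb target, and any increase moves a reading from a lower to a higher dose.

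The effect on a rate depends on the reading moved. Take a column with k outliers in m readings. Losing an outlier changes k/m to (k − 1)/(m − 1), which is lower when k < m. Losing a normal reading changes it to k/(m − 1), which is higher when k > 0. The SAP does not say how often outliers occur at dose-change visits, so the net direction is unknown.

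**3. Head count at Week 6, if the rule is applied there.** Inputs from section 3.1: 3 tablet-count groups of 16, allocated 3:1 to vadadustat or placebo.

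- Vadadustat per group: 16 × 3/4 = 12, so 3 × 12 = 36 in total.
- Placebo per group: 16 × 1/4 = 4, so 3 × 4 = 12 in total.
- This reproduces the 12 subjects in each of 4 treatment groups in section 4.10.
- By treatment taken up to Week 6: 12 placebo and 36 vadadustat readings, before any earlier reductions or interruptions.
- By latest dose at Week 6: 0 placebo and 48 vadadustat readings.
- Share of readings credited to vadadustat that come from placebo subjects: 12/48 = 25%.

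**4. What 25% could do to a rate.** The SAP gives no outlier rates, so those below are assumptions. With p0 on placebo and p1 on vadadustat, the apparent vadadustat rate at Week 6 is (36 × p1 + 12 × p0)/48.

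| Assumed p0 | Assumed p1 | Apparent vadadustat rate |
|---|---|---|
| 5% | 10% | 8.8% |
| 5% | 20% | 16.3% |
| 5% | 30% | 23.8% |
| 10% | 30% | 25.0% |

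**5. Primary comparison.** With n = 12 per group, a difference of 1.35 g/dL and SD 0.68 g/dL, power is 99.6% by the noncentral t on 22 df (99.8% by the normal approximation). This agrees with the figure above 95% in section 4.10. Nothing in 4.9.2 enters this calculation.

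**The case against.** The strongest objection concerns Week 6. Section 4.9.2 never mentions placebo. It splits results by period, and section 3.1 ends the primary period at Week 6 and switches placebo subjects after that period is complete. On that reading their Week 6 values stay under placebo. The footnote that puts the start of vadadustat at the Week 6 visit concerns excess Hb responders. This objection stands: the Week 6 consequence is one possible reading, and the 25% depends on it.

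A reader might infer that high doses are made to look cleaner. The documents do not support this. Dose cuts in the primary period are triggered by Hb, not by the outlier variables, and increases after Week 6 misfile in the opposite direction. The criteria are also worded as any value in a band, so an outlier on 600 mg at a visit before the change still counts under 600 mg.

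A reader might also express the error as a fraction of each subject's readings. That needs the visit schedule for these measurements, which the SAP leaves to the protocol. A share within each starting-dose column would further assume that placebo subjects keep their tablet count at the switch, and the figure showing this is not available.

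Nor does the SAP say that 0 mg is pooled with placebo. It is silent on whether the two are kept apart.

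Finally, the definition is loosely worded: it assigns a visit to a dose and does not state outright that the readings at that visit follow. But the analysis sorts outliers by that label and the SAP offers no other rule, so the example has no other plain reading. Displays by treatment group elsewhere (abnormal chemistry counts in 4.8.4.7, vital signs in 4.8.5.1) soften the consequence. They do not correct this table.

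**Conclusion.** The point holds for readings taken at dose-change visits. As written, 4.9.2 counts them under the dose that begins there, or under 0 mg, and so misattributes by-dose outlier counts. Readings move downward in dose at reductions and interruptions and upward at increases after Week 6. The net effect on outlier rates cannot be established from the document.

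The only size the SAP supports is conditional. If the rule also governs the Week 6 switch, up to 12 of 48 planned Week 6 readings credited to vadadustat (25%) come from subjects who had taken only placebo. This assumes full planned enrolment and a reading from every subject at Week 6. If the period split keeps those readings under placebo, the figure is zero.

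This should be fixed, but it is not critical. The table is descriptive, and the primary analysis, alpha and power are unaffected.

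**What to change.** Reword 4.9.2 on three points:

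- Define the analysis dose of each reading as the dose in effect during the interval ending at that visit. In the SAP's example the Week 4 reading then counts under 600 mg, and 450 mg begins with the next reading. State how a dose change between visits is handled.
- State that the Week 6 readings of placebo subjects remain under placebo.
- Use 0 mg only for readings taken while vadadustat is off, and show that class separately from randomised placebo.

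The cost is a few lines of SAP text and one change to the derivation of the dose label. It needs no new data and changes no dosing rule.

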### **4.2 General Presentation Considerations**

'Pre-treatment' of Hb is defined as the average of 2 Hb values obtained prior to treatment based on the qualifying screening Hb value and the Hb value at the Baseline Visit. 'Pre-

treatment' for other variables is defined as the last available pre-treatment assessment. In general, this is the value at the Baseline Visit. 'End of Treatment (EOT)' is defined as the assessment on the EOT form labeled as 'Week 16 Visit', even if other values closer to Day 113 are available. 'Treatment Day' will be calculated relative to start of dosing at Baseline Visit (i.e. Treatment Day = Assessment Date - Baseline Visit Date + 1).

Continuous data will be summarized in terms of the mean, standard deviation (SD), median, minimum, maximum and number of observations, unless otherwise stated. The minimum and maximum will be reported to the same number of decimal places as the raw data recorded in the database. The mean and median will be reported to one more decimal place than the raw data recorded in the database. The SD will be reported to two more decimal places than the raw data recorded in the database. In general, the maximum number of decimal places reported shall be four for any summary statistic.

Categorical data will be summarized in terms of the number of subjects providing data at the relevant time point (n), frequency counts and percentages. Any planned collapsing of categories will be detailed in the SAP text and the data displays.

Percentages will be presented to one decimal place. Percentages will not be presented for zero counts. Percentages will be calculated using n as the denominator. If sample sizes are small, the data displays will show the percentages, but any textual report will describe frequencies only.

Changes from baseline in categorical data will be summarized using shift tables where appropriate.

P-values greater than or equal to 0.001, in general, will be presented to three decimal places. P-values less than 0.001 will be presented as "<0.001".

Confidence intervals will be presented to one more decimal place than the raw data.

All report outputs will be produced using SAS® version 9.3 or a later version in a secure and validated environment. All report outputs will be provided to the Sponsor in a single Microsoft Word 2010 [Version 14.0] document.

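### In the maintenance-period outlier tables, changes that arose on placebo are counted under a vadadustat dose, because switched placebo subjects keep their Day 1 reference

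*SAP*

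**What the plan says.** The references are to the current SAP text (Amendment 3).

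- **Purpose of the table.** Section 4.9.2 sets out to "identify the treatment Emergent outliers by each prescribed dose at each period". The classification is by dose in force, not by randomised arm.
- **Coverage.** "The following components will be analyzed by primary efficacy period and dose adjustment and maintenance period for all subjects", and again for the subset whose values were not elevated at baseline (for example systolic pressure below 140 mmHg).
- **Criteria.** Besides absolute thresholds, each variable has rows for a rise from baseline, for example "Any Potassium increase from baseline >1.0 to 1.5 mEq/L".
- **Exclusion of earlier findings.** "Only treatment-emergent outliers will be counted but outliers at the baseline and screening visits will be excluded".
- **Reference value.** Section 4.9.2 does not define baseline. Section 4.2 says that the pre-treatment value "for other variables is defined as the last available pre-treatment assessment", and adds: "In general, this is the value at the Baseline Visit". Section 3.1 places that visit on Day 1.
- **Switch.** Section 3.1, on the period after Week 6: "Subjects receiving placebo will be switched to vadadustat".

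**The concern.** A table of treatment-emergent outliers by vadadustat dose should show what emerged after vadadustat was started. For a subject randomised to vadadustat, the Day 1 value precedes the drug. For a subject randomised to placebo, Day 1 precedes six weeks of placebo, and any change over those weeks is carried into the vadadustat rows. The same subject also enters or misses the non-elevated subset on a value taken six weeks before the first vadadustat dose.

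Blood pressure and potassium matter here: Section 4.8.2 lists hypertension and hyperkalemia among the adverse events of special interest. Because 4.9.2 pools by dose, a reader of the table cannot tell switched subjects from the rest. With only 48 planned subjects spread over several doses, one or two subjects can visibly change a dose row.

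**Working it through.** **1. How many subjects.** Section 3.1: 48 subjects, three tablet-count groups, 3:1 vadadustat to placebo within each. 48/3 = 16 per group; 16 × 1/4 = 4 on placebo; 3 × 4 = 12. This reproduces the 12 per treatment group in Section 4.10. Share affected: 12/48 = 25%.

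**2. How many rows.** Increase-from-baseline rows: systolic 2, diastolic 2, pulse 2, potassium 3, total 9. The non-elevated subset is affected throughout. The absolute-threshold rows have a related gap: a value that first crosses the threshold on placebo and persists is removed only if it was already present at screening or baseline.

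**3. Tracing one subject (illustrative values).**
- Systolic 130 on Day 1, 152 at the end of placebo, 152 on vadadustat. From Day 1: 152 − 130 = +22, counted in the 20 to below 40 row. From the last pre-vadadustat value: 152 − 152 = 0, not counted. The subject is in the non-elevated subset (130 < 140) although at 152 when vadadustat started.
- The reverse: 152 on Day 1, 130 at the end of placebo, 152 on vadadustat. From Day 1 the change is 0, not counted; from the last pre-vadadustat value it is +22. The subject is left out of the non-elevated subset although at 130 when vadadustat started.

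So the misattribution runs both ways.

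**4. Size, one reading.** The SAP gives no standard deviations for these variables, so all those below are assumptions. With no drug effect, within-period change SD σ and a lasting shift on placebo of SD s, P(rise ≥ c) = 1 − Φ(c/√(σ² + s²)) from Day 1, and the same with s = 0 from the pre-vadadustat value.
- Systolic, c = 20, σ = 12: 4.8% with s = 0; 6.8%, 8.3% and 10.0% with s = 6, 8 and 10. Excess in 12 subjects: 12 × (0.068 − 0.048) = 0.24 to 12 × (0.100 − 0.048) = 0.62.
- Potassium, c = 0.5, σ = 0.4: 10.6% with s = 0; 13.2% to 18.8% with s = 0.2 to 0.4. Excess: 12 × (0.132 − 0.106) = 0.31 to 12 × (0.188 − 0.106) = 0.98.

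**5. Size, any reading.** Section 4.9.2 counts any qualifying reading, so systolic pressure was also simulated with no drug effect, five later visits (assumed), within-subject SD 8 to 12 mmHg and a lasting zero-mean shift on placebo of SD 0 to 8. Probability of any rise of at least 20 mmHg:

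| Within SD | Shift SD | From Day 1 | From Week 6 | Difference × 12 subjects |
|---|---|---|---|---|
| 8 | 0 | 13.2% | 13.4% | −0.02 |
| 8 | 8 | 19.6% | 13.3% | 0.76 |
| 10 | 8 | 28.1% | 24.2% | 0.47 |
| 12 | 0 | 33.4% | 33.4% | 0.00 |
| 12 | 8 | 35.4% | 33.5% | 0.23 |

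The net change is below one expected subject and vanishes without a lasting shift. The gross figure is somewhat larger. Between 2.2% and 11.6% of placebo subjects were already at least 20 mmHg above Day 1 at Week 6 and were counted again under vadadustat, which is 12 × 0.022 = 0.26 to 12 × 0.116 = 1.39 subjects. Part of that is visit-to-visit noise.

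**The case against.** The strongest defence is that one Day 1 reference for everyone is a coherent choice. A lasting non-drug shift over Weeks 1 to 6 would affect the 36 vadadustat-randomised subjects as well, and their maintenance-period rises are also measured from Day 1. Moving only the 12 to a later reference puts a window of roughly 10 weeks beside one of 16 weeks in the same dose row. This stands against re-baselining alone, and it is why the switched subjects should also be displayed separately. It does not rescue the present text: for the 36, the whole time since Day 1 follows the start of vadadustat, while for the 12 the first six weeks do not.

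It can also be said that the table is descriptive, carries no test or decision rule, and that Sections 4.8.4.7 and 4.8.5.1 summarise the same variables by treatment group and time point with listings. If those groups are the randomised ones, drift on placebo can be seen there. This limits the harm and stands.

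One might read pre-treatment in Section 4.2 as pre-vadadustat. The sentence that ties it to the Baseline Visit, and the counting of Treatment Day from dosing at that visit, speak against this.

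Three stronger readings are tempting but unsupported:
- That vadadustat rates are necessarily inflated. This needs a lasting upward or variance-adding shift on placebo; a fall on placebo would mask increases.
- That particular dose rows suffer most. The doses at which placebo subjects start after Week 6 are not in the SAP text shown.
- That the Week 6 visit supplies the right reference. The SAP text does not say that these variables are measured then; it refers to the protocol for the schedule.

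**Conclusion.** The point holds as a misattribution. Following Sections 3.1, 4.2 and 4.9.2 together, change that arose on placebo in up to 12 of 48 subjects is reported under a vadadustat dose, contrary to the purpose of the section. The direction is open. The magnitude rests wholly on assumed SDs, shifts and visit numbers; in the scenarios examined (systolic rise of at least 20 mmHg, potassium rise above 0.5 mEq/L) the net effect is below one expected subject per criterion. The placebo-controlled table for the primary efficacy period and the primary hemoglobin analysis are unaffected. It is a cheap improvement of minor severity.

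**What to change.** Add to Section 4.9.2 that, in the dose adjustment and maintenance period:

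- for subjects randomised to placebo, baseline is the last available value before the first vadadustat dose, both for the increase-from-baseline rows and for membership of the non-elevated subset;
- for subjects randomised to vadadustat, baseline remains the Day 1 value;
- former placebo subjects are shown separately, or at least footnoted, so that different observation windows are not pooled in one dose row.

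The cost is one derived baseline variable, an extra column or sub-table, and smaller cells. No data collection or clinical procedure changes.

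### SAP 4.9.2 sets non-elevated baseline potassium at <4 mEq/L, 1.5 mEq/L below the first absolute outlier band, so the label, the subset and its absolute rows do not fit together

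*SAP*

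**What the plan says.** Section 4.9.2, added by SAP Amendment 3, counts treatment-emergent outliers by prescribed dose within the primary efficacy period and within the dose adjustment and maintenance period. It does this "for all subjects and for subjects with non-elevated values at baseline". The baseline definitions include "Systolic Blood Pressure <140 mmHg", "Diastolic Blood Pressure <90 mmHg", a heart rate below 100 bpm and "Potassium <4 mEq/L".

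Six potassium criteria follow. Three are absolute: "Any Potassium >5.5 to 6.0 mEq/L", then above 6.0 to 6.5, then above 6.5 mEq/L. Three are rises: "Any Potassium increase from baseline >0.5 to 1.0", "Any Potassium increase from baseline >1.0 to 1.5 mEq/L" and "Any Potassium increase from baseline > 1.5 mEq/L". All six apply to both populations.

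The change list in Section 5.1.1.3 (Change #13) carries the same potassium cut-off, so the figure is not a text-extraction slip.

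**The concern.** A subset defined as not elevated at baseline exists to show who becomes elevated on treatment. Its entry cut-off should therefore separate subjects who are already high from those who are not. At <4 mEq/L it does not: a baseline of 4.5 is treated as if it were elevated, although the lowest absolute band starts above 5.5. A subject who goes from 4.5 to 5.7 newly crosses the plan's own threshold but cannot appear in the subset.

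Potassium is a safety topic that the plan singles out. Section 4.8.2 lists hyperkalemia and increased blood potassium as adverse events of special interest. Amendment 3 (Change #10) also dropped the dedicated count of subjects with a potassium above the upper limit of normal, so Section 4.9.2 is now the only place with potassium-specific laboratory thresholds. A reader may take few or no subjects in the subset's absolute rows as evidence of few new elevations, when the entry rule itself contributes to that result.

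**Working it through.** The SAP states no size or expected count for this subset, so there is no figure to reproduce. The check has three steps.

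**1. Gap between the baseline cut-off and the first absolute band.** All inputs are from Section 4.9.2. Gap = start of the first absolute band minus the baseline cut-off.

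| Component | Cut-off | First absolute band starts | Gap | Lowest change band starts | Highest change band starts |
|---|---|---|---|---|---|
| Systolic pressure (mmHg) | 140 | 160 | 20 | 20 | 40 |
| Diastolic pressure (mmHg) | 90 | 100 | 10 | 10 | 20 |
| Heart rate (bpm) | 100 | 100 | 0 | 20 | 30 |
| Potassium (mEq/L) | 4.0 | 5.5 | 1.5 | 0.5 | 1.5 |

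For both pressures the gap equals the start of the lowest change band. For heart rate it is zero. For potassium it equals the start of the highest change band and is 1.5 / 0.5 = 3 times the lowest.

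**2. Which rows a subset member can enter.** Let the baseline be b < 4.0 and an on-treatment value be v.

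- An absolute band needs v > 5.5, so v - b > 5.5 - 4.0 = 1.5. Everyone in an absolute band is therefore also in the >1.5 change band.
- The change bands depend only on v - b. From b = 3.8, a rise of 0.6 falls in >0.5 to 1.0 and a rise of 1.2 falls in >1.0 to 1.5. These rows work.
- The lower the baseline, the larger the rise needed: from 3.6, a rise of 1.6 gives 5.2 and enters no absolute band.

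**3. Share of subjects in the subset.** The SAP gives no potassium distribution. The means and SDs below are assumptions, with a normal distribution: P(b < 4) = Φ((4 - mean) / SD). For example, a mean of 4.2 and an SD of 0.5 give Φ(-0.4) = 34.5%. The 48 planned subjects are from Section 4.10.

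| Assumed mean | SD 0.4 | SD 0.5 | SD 0.6 | Of 48 |
|---|---|---|---|---|
| 3.8 | 69% | 66% | 63% | 30-33 |
| 4.0 | 50% | 50% | 50% | 24 |
| 4.2 | 31% | 35% | 37% | 15-18 |
| 4.4 | 16% | 21% | 25% | 8-12 |
| 4.6 | 7% | 12% | 16% | 3-8 |
| 4.8 | 2% | 6% | 9% | 1-4 |
| 5.0 | 1% | 2% | 5% | 0-2 |

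These are totals. Section 4.9.2 tabulates by prescribed dose and period, and under Section 3.1 placebo subjects switch to vadadustat after Week 6 and doses are adjusted, so dividing by four randomised arms would not give the table's cells.

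**Effect of a different cut-off.** The blood pressure pattern, one lowest change band below the first absolute band, gives 5.5 - 0.5 = 5.0 mEq/L. Under assumed means of 4.2 to 4.8 and SDs of 0.4 to 0.6, <5.0 keeps about 63-98% of subjects, against 2-37% at <4.

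**The case against.** The strongest reply is that no potassium signal would be lost. The same six criteria are run in all subjects, where every treatment-emergent value above 5.5 is counted whatever the baseline. Section 4.8.4.7 keeps potassium values, changes and abnormal-value counts by group and time point, with a listing. Section 4.8.2 keeps the special-interest adverse event summary. The subset carries no test and no decision rule. All of this stands, and it limits the severity.

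Three stronger readings are tempting, and the SAP does not support them.

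- A reader might infer that the subset can register only rises above 1.5 mEq/L. That is true of its absolute rows only; the change rows count rises from just above 0.5.
- A reader might infer that the cut-off drops most subjects. That follows only if the median baseline potassium is above 4.0, and the SAP does not give it. At an assumed mean of 3.8, most subjects are kept.
- A reader might infer that the potassium analysis as a whole will be nearly empty and falsely reassuring. The all-subjects table and the other potassium displays rule that out.

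It can also be said that no replacement value is dictated by the text: the SAP states no upper limit of normal, and the three sibling components do not share one rule. That is fair. It bears on which number to choose, not on whether <4 fits its label.

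**Conclusion.** Wrong as written, at minor severity. The mismatch rests on Section 4.9.2 alone and needs no outside data: the potassium cut-off is 1.5 mEq/L below the first absolute band, it excludes baselines of 4.0 to 5.5 that no absolute band counts as outlying, and it makes the subset's absolute rows depend on a rise already captured by the top change row. How many subjects are affected does depend on assumptions, and the results run from about two thirds kept to almost none kept across assumed means of 3.8 to 5.0. The consequence is confined to one descriptive safety subset; the primary and secondary efficacy analyses are untouched.

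**What to change.** Before unblinding, replace the <4 mEq/L cut-off in Section 4.9.2 with one that matches the label. Two choices are defensible: at or below the laboratory's upper limit of normal for potassium, with the value stated in the SAP, or <5.0 mEq/L, which follows the systolic and diastolic pattern. Either lets the subset's absolute rows count subjects who newly become elevated. If <4 was intended, give the reason, rename the subset so that it is not described as non-elevated, and note under the table that its absolute rows require a rise above 1.5 mEq/L.

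The cost is one number in the SAP and in the table program, with the matching footnote. No data collection changes.
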